## X. STATISTICAL ANALYSIS

Based on the sample size calculations below, a total of 30 patients should be sufficient to demonstrate statistical non-inferiority of the Harpoon Medical device to other devices currently on the market in the EU for less-invasive mitral valve repair in the beating heart with a 90% power using a two-sided  $\alpha$  of 0.05 (one-sided 0.025). The clinical investigation of the Harpoon Medical device involves a multi-center study conducted across multiple countries and up to a total of 20 patients will be enrolled in the UK. Data collected from the first 30 patients enrolled across all sites will be used to support the CE mark of the Harpoon Medical device. Therefore, data from some or all of the 20 patients enrolled in the UK, depending on the timing of enrollment, will be used to support the CE mark of the Harpoon Medical device. The estimated enrollment period for the study is up to 24 months, and all patients shall be followed for 30 days, 6 months, 12 months, 18 months, 24 months, 30 months, 36 months, 48 months and 60 months after implantation in accordance with the Clinical Investigations schedule provided in Section VIII.

Currently, there are two (2) Class III reference devices on the market in the EU for treating MR due to one or more prolapsed leaflets (degenerative MR): the MitraClip device and the NeoChord DS1000. Both of these devices were designed to reduce MR on a beating heart without the need to arrest the heart or place the patient on cardiopulmonary bypass. The primary and secondary endpoints used to support CE mark for these devices were: freedom from death and MACE, freedom from surgery for mitral valve repair or replacement, and a reduction of MR to grade  $\leq 2$ . The studies performed in support of CE mark for both the NeoChord and MitraClip devices reported 30 day response rates.

For the MitraClip device, data following treatment with the MitraClip implant demonstrated a success rate for mitral regurgitation reduction to  $\leq$  grade 2 in 58% (14/24 patients) at 30 days, and 54% at 6 months (13/24 patients) (Feldman et al., 2005). In a subsequent randomised trial of MitraClip compared to surgical treatment of mitral valve regurgitation, the success rate was 55% at 12 months (100/181 patients) (Feldman, et al., 2011).

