For the initial CE Mark Study of the NeoChord DS1000, data from 30 patients at seven (7) study centers at 30 days post-implant was evaluated in support of the CE Mark. In this study, the primary composite outcome was assessed in patients in whom at least one chordae tendineae was placed using the NeoChord DS1000 System. The composite endpoint consisted of the following elements:

- a reduction in mitral regurgitation  $\leq 2+$  at the time of the procedure AND
- MR reduction of  $\leq 2+$  at 30 days AND
- The rate of Major Adverse Events (MAE) defined as a combined endpoint of: death, MI, reoperation for failed surgical repair, non-elective cardiovascular surgery to treat an adverse event, procedural ventilation  $> 48$  hours, procedure-related transfusion of  $> 2$  units blood product, stroke, renal failure, deep wound infection, new onset of permanent AF, and septicemia, through 30 days.

Based on this definition, the response rate was 57% (17/30 patients) (Seeburger et al., 2014). In two subsequent single-center reports, the composite success rate using the NeoChord DS1000 was 85% (11/13 patients) at 6 months post-procedure (Rucinskas, et al., 2014) and 87% (54/62 patients) at 30 days post-procedure (Colli, et al., 2015). Combining these results, irrespective of the time of assessment of the primary endpoint, the average success rate among these studies is 68%, the standard deviation of the response rate is 15%, and the lower limit of one-sided 95% confidence intervals (CI) is approximately 50%.

An inferiority margin of 10% was selected as appropriate because it is a more stringent requirement than the lower bound of the 95% confidence interval of the average response rates in these previous studies. This non-inferiority delta reflects the diversity of the patients treated, the diversity of the causes of MR, the variety of non-beating heart methods available to treat MR, and the range of reported performance using similar techniques.

Using the historical control (HC) rate of 68% and a non-inferiority margin of 10%, the null and alternative hypotheses of the primary performance endpoint can be written as:

$$H_0: \pi_{\text{Harpoon\_performance}} \leq \pi_{\text{HC\_performance}}$$

$$H_A: \pi_{\text{Harpoon\_performance}} > \pi_{\text{HC\_performance}}$$

where,

$$\pi_{\text{HC\_performance}} = 68\% \text{ historical control rate} - 10\% \text{ Delta}$$

$$\pi_{\text{Harpoon\_performance}} = \text{Harpoon Medical system success rate}$$

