The hypotheses for the primary performance endpoint can be rewritten as:

$$H_0: \pi_{\text{Harpoon\_performance}} \leq \text{HC \%}$$

$$H_A: \pi_{\text{Harpoon\_performance}} > 58\%$$

To achieve 90% power using a two-sided  $\alpha$  of 0.05 (one-sided 0.025), the sample size was estimated based on a single sample compared to a constant (0.58). Based on this calculation, 26 patients are required to demonstrate non-inferiority. To adjust for patients lost to follow-up, we have decided to enroll up to 30 patients in the TRACER Trial. Moreover, 30 patients has been a sufficient number of patients to provide a satisfactory profile of the adverse events likely to occur with beating heart mitral valve repairs in the aforementioned studies. Last, 30 patients is consistent with the sample size of previous beating heart, mitral valve repair devices. For example, the CE mark trial of the NeoChord DS1000 was conducted in 30 patients.

These data from these 30 patients shall be used to assess the safety and performance of the device when used on a human patient. All data shall be captured on an intent-to-treat basis. Data shall be reported as descriptive statistics.

The percentage of patients with improvements in MR reduction at the conclusion of the procedure, at the time of the hospital dismissal and at 30 days, six months, one, two, three, four and five years will be assessed. Specifically the percentage of patients that demonstrate MR reduction from “severe” to less than or equal to “moderate” at the conclusion of the procedure and at 30 days. While the number of subjects missing the primary endpoint of improvement in MR is anticipated to be small, if any, the following algorithm will be used to impute missing observations:

- Subjects who die prior to evaluation at 30 days or fail the procedure will be considered failures for the primary analysis.
- Patients lost after the procedure for other reasons will have their last observation carried forward (from procedure to 30 days). Should this situation occur, an additional sensitivity analysis, a tipping point analysis, will be conducted whereby each subject missing 30 day follow-up will be counted as a failure in succession, and the number of subjects with

missing data imputed as failures which “tip” the analysis to non-significance will be reported.

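### Section X claims 90% power with 26 patients (30 enrolled) but gives neither the test nor the assumed true Harpoon rate; at the plan's own 68%, power is about 11–23%, and 90% needs a true rate of about 81–87%

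*Combined protocol and SAP*

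**What the plan says.** All of this is in Section X, Statistical Analysis.

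- **Claim.** The opening says "a total of 30 patients should be sufficient to demonstrate statistical non-inferiority of the Harpoon Medical device to other devices" already marketed in the EU, with 90% power at two-sided 0.05 (one-sided 0.025). Later: "Based on this calculation, 26 patients are required to demonstrate non-inferiority". Enrolment of 30 is meant to cover losses to follow-up.
- **Reference rate.** From the published MitraClip and NeoChord results, "the average success rate among these studies is 68%, the standard deviation of the response rate is 15" percent.
- **Threshold.** The 68% less a 10-point margin gives 58%. The alternative hypothesis is only that the Harpoon rate exceeds 58%; the Harpoon rate itself remains a symbol.
- **Method.** The only description is that "the sample size was estimated based on a single sample compared to a constant (0.58").
- **Endpoint.** "The percentage of patients with improvements in MR reduction at the conclusion of the procedure" and at later times is assessed. The primary criterion is MR falling from severe to moderate or less at the end of the procedure and at 30 days, so each patient is a success or a failure.
- **Significance.** If 30-day data are missing, "an additional sensitivity analysis, a tipping point analysis, will be conducted", reporting how many imputed failures would turn the result non-significant.

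**The concern.** Power is a function of the true rate. A 90% figure with no rate attached cannot be interpreted, and here it is the stated reason that 30 patients are enough.

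The size also looks too small. Distinguishing 68% from 58% on a yes/no outcome normally takes a few hundred patients, not 26. The one standard deviation printed, 15%, describes how published study rates differ from one another. It is not the variability of a single patient's outcome.

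What is at stake is the reading of a result that does not reject the null. If the true rate were 68%, a trial of 30 would fail to reject 79% of the time (score test, 1 − 0.208) to 89% of the time (exact test, 1 − 0.110). No part of the plan says non-rejection means inferiority, but a stated 90% power invites that reading.

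**Working it through.** **Inputs, all from Section X:** null rate 0.58 (68% − 10%); one-sided alpha 0.025; target power 90%; printed SD 0.15; n = 26 and 30; binary endpoint. The true rate is not given. I take 0.68 as one scenario and then solve for the rate that gives 90%.

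**1. Reproducing 26.** One-sample t-test on a mean (noncentral t), difference 0.10, SD 0.15, standardised difference 0.10/0.15 = 0.667:

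- n = 25: power 89.2%
- n = 26: power 90.4%
- n = 30: power 94.2%

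So 26 is the first n that reaches 90%. The normal approximation, (1.960 + 1.282)² × 0.15²/0.10² = 23.6, would give 24.

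**2. The SD.** At a true rate of 0.68 the SD of a yes/no outcome is √(0.68 × 0.32) = 0.466, about three times 0.15. The same t-test with 0.466 has power 18.2% at n = 26 and 20.5% at n = 30, and needs n = 231 for 90%. The cited study rates are 14/24, 13/24, 100/181, 17/30, 11/13 and 54/62. Their unweighted SD across all six is 0.141 (divisor n) or 0.154 (divisor n − 1), so the printed 15% is of the size of a between-study spread.

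**3. Proportion formulas at 68% versus 58%.**

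- Score: n = [(1.960√(0.58 × 0.42) + 1.282√(0.68 × 0.32))/0.10]² = 245.
- Wald: n = (1.960 + 1.282)² × 0.68 × 0.32/0.10² = 229.
- Exact binomial: 90% is first reached at n = 247.

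None gives 26.

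**4. Power of the actual decision rules** (binomial tail probabilities; size is the probability of rejecting at 58%).

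| n | Rule | Reject if at least | Size | Power at 68% | True rate for 90% power |
|---|---|---|---|---|---|
| 26 | Exact or score | 21/26 | 1.3% | 11.5% | 87.4% |
| 26 | Wald | 20/26 | 3.6% | 22.6% | 84.3% |
| 30 | Exact | 24/30 | 1.0% | 11.0% | 86.5% |
| 30 | Score or Wald | 23/30 | 2.7% | 20.8% | 83.8% |

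The upper end of the power range belongs to rules whose actual size exceeds 2.5%. Solving the approximate formulas for the rate that gives 90% power yields 82.3% (Wald) to 85.8% (score) at n = 26, and 81.2% to 84.2% at n = 30. Over all versions the required true rate is about 81–87%.

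**5. The other route to 26.** A proportion formula gives about 26 if the assumed true rate is in the 80s: the Wald formula gives 26.9 at 82% and 23.7 at 83%; the score formula gives 27.9 at 85% and 25.4 at 86%.

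**6. Power by true rate, n = 30.**

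| True rate | 68% | 75% | 80% | 85% | 90% |
|---|---|---|---|---|---|
| Exact (24/30) | 11% | 35% | 61% | 85% | 97% |
| Score (23/30) | 21% | 51% | 76% | 93% | 99% |

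**The case against.** The strongest reply is that 68% is the control rate used to build the threshold, not the rate expected of Harpoon. The sponsor may have expected more: "the composite success rate using the NeoChord DS1000 was 85% (11/13 patients) at 6 months post-procedure", another single-centre report gave 87%, and this trial excludes anterior and bileaflet prolapse. With a true rate in the mid-80s, 26 to 30 patients can be adequate, and the t-test origin of 26 is an inference. This stands to the extent that the documents cannot separate the two routes, and 11–23% is power in one scenario. It does not rescue the text: no such rate is stated, and at 80% the exact test with 30 patients still has only 61% power.

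A second reply is that Section X calls the data descriptive and, after the SAE paragraphs, says no hypothesis test or formal sample size was intended. Yet the same section sets out hypotheses, alpha, power, a sample size and a tipping-point analysis keyed to loss of significance. If the descriptive statements govern everything, the section contradicts itself and the 90% should not be there.

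A third reply is that little can change now. The Study Summary says enrolment ended in November 2017, and Potential Risks records the CE mark in December 2017. That is right, and it limits the point to correct reporting. Once data exist, the observed rate and its interval carry the inference, and low power does not inflate false positives.

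**Conclusion.** The concern holds. The unconditional 90% power statement is wrong as written. For the binary endpoint, against 58% at one-sided 0.025, power at a true 68% is 11.5–22.6% with 26 patients and 11.0–20.8% with 30. Reaching 90% requires a true rate of about 81–87%, or about 245 patients at 68%.

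The omission of test and true rate is certain, and so are the conditional figures. Whether the underlying fault is an arithmetic error (the 15% used as a patient-level SD) or an undisclosed assumption cannot be settled from the documents. The exact match at 26 with the two printed inputs makes the first a serious possibility. A rejection of the null is unaffected; what the 90% cannot support is reading a non-rejection as evidence of inferiority.

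**What to change.** No added patients.

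1. **Disclose the basis of 26:** the test, SD and true rate actually used, or a statement that they cannot be recovered. If the 15% served as a patient-level SD, say so and correct it. Do not insert a mid-80s rate now as if it had been the planning assumption.
2. **Replace the unconditional 90%** in both places with power conditional on the true rate. For example: *Recalculated after enrolment closed: with 30 patients and a one-sided exact binomial test of 58% at 0.025 (reject if at least 24/30; actual size 1.0%), power is 11%, 35%, 61%, 85% and 97% at true rates of 68%, 75%, 80%, 85% and 90%.* For a score test (23/30; size 2.7%) the figures are 21%, 51%, 76%, 93% and 99%. Name the test used for the first-30 analysis, not one chosen now; the two rules differ only at 23/30.
3. **Report the observed rate with its 95% confidence interval against 58%,** and state that failing to reject would not show inferiority to the 68% reference. For illustration, 22/30 is 73.3% (exact 95% CI 54.1–87.7%): above both 58% and 68%, yet it does not reject.

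The cost is wording in Section X and the final report. The stated power will look less favourable, and the sponsor may have to acknowledge an error in the sample-size calculation.

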#### DEVICE DESCRIPTION

The Harpoon Medical Transapical device is intended to be used to reduce the degree of mitral regurgitation by delivering and anchoring artificial chordae tendineae to the affected mitral valve leaflet(s) in a beating heart. The device is intended to be a Single Use Device, used in a surgical operating suite or equivalent setting. Harpoon Medical has developed a novel small-diameter (< 3 mm) rigid linear delivery system using a needle wrapped with ePTFE in a pre-formed knot configuration. The device delivers replacement chordae using a valved introducer inserted a few centimeters "off apex" using Transoesophageal echocardiography (TOE). To deploy the pre-formed knot on the atrial side, the delivery system is actuated to advance the needle and pre-formed knot through the leaflet. The delivery system then retracts the needle, leaving the pre-formed knot on the atrial side of the leaflet. After deployment, the delivery system is withdrawn from the valved introducer, exposing the replacement chordae tendineae. The procedure may be repeated up to 4 times using a single valved introducer. The replacement chordae tendineae are adjusted under real-time TOE to optimise the surface of coaptation between leaflets before they are secured to an ePTFE pledget on the epicardium.

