##### **PERFORMANCE GOALS**

**Primary Performance Endpoints:** To demonstrate that the Harpoon Medical device performs as designed and has the ability to successfully implant one or more ePTFE chordae tendineae on the mitral valve via a small left thoracotomy on the beating heart and reduce mitral regurgitation from “severe” to less than or equal to “moderate” at the conclusion of the procedure and at 30 days post-procedure.

**Secondary Performance Endpoints:** Severity of mitral regurgitation at 6 months, 12 months, 18 months, 24 months, 30 months, and 36 months follow-up shall be tracked and recorded.

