## FOLLOW-UP PROCEDURES/ASSESSMENTS

**Post-procedure management:** Standard hospital protocols for the management of patients after mitral valve surgery shall be followed. Unless other indications for anticoagulation are present, all patients shall receive only 325 mg/day, beginning on arrival to the intensive care unit).

**Discharge:** All patients shall be discharged from the hospital at the discretion of the attending cardiac surgeon. Prior to dismissal all patients shall undergo a comprehensive pre-dismissal TOE, as well as a physical assessment (vide supra) in accordance with the schedule of Clinical Investigations.

**Patient follow-up:** Patients shall be seen in the outpatient clinic 30 days (+10 days/-0 days) after the Harpoon procedure. A TTE and a clinical assessment shall be performed at that time (in accordance with the schedule of Clinical Investigations) to evaluate the device against the primary and secondary performance and safety endpoints.

Additional clinical and TTE follow-up in a registry fashion shall occur for all active subjects (in accordance with the Clinical Investigations defined in the table below) at the following intervals:

- 6 months (+/- 30 days),
- 12 months (+/- 30 days)
- 18 months (+/- 30 days)
- 24 months (+/- 30 days)
- 30 months (+/- 30 days)
- 36 months (+/- 30 days)
- 48 months (+/- 30 days) and
- 60 months (+/- 30 days)

If due to an increase of MR, or due to any other medical circumstances, and a study patient has to undergo a Mitral Valve reoperation, this patient will be followed up by the study team for 30 days and then will be exited from the study

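### The rule for patients lost before day 30 points to the end-of-procedure MR grade although a discharge echo is scheduled; where the two grades differ, the choice can only favour the device

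*Combined protocol and SAP*

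**What the plan says.** The primary performance endpoint (Section IV, Performance Goals) requires MR at or below moderate at two times: "at the conclusion of the procedure and at 30 days post-procedure".

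Section X gives two rules for patients without a day-30 grade:

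- Deaths and procedural failures: "Subjects who die prior to evaluation at 30 days or fail the procedure will be considered failures for the primary analysis".
- Everyone else: "Patients lost after the procedure for other reasons will have their last observation carried forward (from procedure to 30 days"; the bracket closes there.

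If the second rule is used, a tipping-point sensitivity analysis follows, in which "each subject missing 30 day follow-up will be counted as a failure in succession".

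An MR reading is due between the two endpoint times. Section VII, under Discharge, states: "Prior to dismissal all patients shall undergo a comprehensive pre-dismissal TOE, as well as a physical assessment". The schedule in Section VIII marks a TTE, not a TOE, at discharge. The two places disagree on modality and must be reconciled, but both schedule an echo. Section X also lists the times at which MR improvement is assessed: "at the conclusion of the procedure, at the time of the hospital dismissal and at 30 days".

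**The concern.** The sentence names a method (carry the last observation) and then a source (the procedure). For a patient lost after discharge these are different readings. After the words *carried forward*, a phrase running from one time to another most naturally gives origin and destination. An analyst working only with the two endpoint variables would do just that and copy the first into the second.

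The procedure reading is also a favourable one to carry. It is taken when the repair is being tuned: "The replacement chordae tendineae are adjusted under real-time TOE to optimise the surface of coaptation between leaflets". Section VII adds that a patient whose MR reduction the surgeon judges inadequate is converted to open surgery, at once or later. Most unconverted patients should therefore look satisfactory at that moment. A return of MR by discharge is the early signal that the bracket would pass over.

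At stake is the primary count in a 30-patient data set intended to support the CE mark. If both readings are tenable, two analysts could score the same patient differently on the primary endpoint.

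**Working it through.** **Step 1. Score the possible records.** Success needs a grade at or below moderate at the end of the procedure and at day 30. For a patient lost before day 30, other than by death or procedural failure:

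| End of procedure | Discharge | Bracket (procedure grade carried) | Latest grade carried |
|---|---|---|---|
| ≤ moderate | ≤ moderate | success | success |
| ≤ moderate | severe | **success** | **failure** |
| ≤ moderate | no echo | success | success |
| severe | any | failure | failure |

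The readings differ in one row only, and there the bracket gives the success. Successes under the latest-grade rule are a subset of successes under the bracket, so the difference cannot go against the device.

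**Step 2. The plan's sample size.** Inputs from Section X: null rate 68% − 10% = 58%, one-sided α 0.025, power 90%, 26 patients required, 30 enrolled. The assumed true success rate p1 is not stated, so 26 cannot be reproduced from the plan's own inputs. Solving backwards with

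n = [(1.96·√(0.58·0.42) + 1.28·√(p1(1−p1))) / (p1 − 0.58)]²

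gives 27.9 at p1 = 0.85, 25.4 (26 when rounded up) at 0.86 and 23.3 at 0.87. The plan's figure therefore implies p1 of about 0.86. Nothing below depends on this. The gap between enrolled and required is 30 − 26 = 4 patients.

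**Step 3. What one patient is worth.** 1/30 = 3.3 percentage points.

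**Step 4. The decision boundary at n = 30.** The plan names no test, so two were tried.

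*Exact binomial*, p = P(X ≥ r | n = 30, π = 0.58):
- r = 24: p = 0.0099, passes
- r = 23: p = 0.0269, does not pass (limit 0.025)

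*Normal test with null variance*, z = (r/30 − 0.58)/√(0.58·0.42/30), where the denominator is 0.0901:
- r = 23: (0.7667 − 0.58)/0.0901 = 2.07, passes (limit 1.96)
- r = 22: (0.7333 − 0.58)/0.0901 = 1.70, does not pass

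Under either test one re-scored patient reverses the result, but only if the count sits exactly on the boundary (24 for the exact test, 23 for the normal test).

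**Step 5. How many patients are affected.** The documents do not say. They give neither the number lost before day 30 nor any discharge grades.

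**The case against.** **The words *last observation* govern, and the bracket only marks the interval.** On that reading the discharge echo is carried and the patient in the second row is a failure. This stands in part: no sentence says the discharge echo is skipped. A reader might infer that the plan deliberately overrides a later, worse grade, but the text supports only a conflict within one sentence. The interval reading is the weaker one, because the sentence already limits itself to patients lost after the procedure and the bracket would then add little.

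**Other provisions cover the case.** The tipping-point analysis eventually counts every such patient as a failure, and MR at dismissal is reported separately, so early recurrence would not be hidden. Both are true, but neither alters the primary count. The category for patients who fail the procedure might catch some, but it is not defined and cannot be relied on.

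**A patient severe at discharge has not failed the endpoint.** This is correct. A reader might infer that any lost patient with an earlier grade above moderate should be failed outright. The documents do not support that: discharge is not an endpoint time, and an observed patient who is severe at discharge and moderate at day 30 is a success. The discharge grade matters only because it is the latest information on a patient with no day-30 reading.

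**The effect on type I error is large.** A reader might suppose that every lost patient is an automatic success and compute an inflated error rate. That would measure the worst case for carrying forward any success. Lost patients at or below moderate at discharge score as successes under both readings, so the result would not be the cost of passing over the discharge echo.

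**It is late to change the rule.** Enrolment ended by November 2017 and the CE mark followed in December 2017, so the day-30 data exist. This is a fair point, and it is why disclosure of the rule actually used belongs in the fix.

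**Conclusion.** The point holds as a conflict in the primary missing-data rule. Its more natural reading uses the end-of-procedure grade where a later one should exist, and the resulting difference can only favour the device. The effect is 3.3 points per affected patient, and it changes the verdict only at the boundary shown above.

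This rests on three assumptions:

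- At least one patient was lost between discharge and day 30 with a discharge grade above moderate. The number is unknown, and Section X expects few missing observations, if any.
- A formal test against 58% is carried out. Section X sets out hypotheses, and its tipping-point analysis looks for loss of significance, but the section also says that data will be reported descriptively.
- The test is one of the two tried here.

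The documents do not show that any patient was mis-scored.

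**What to change.** In Section X, replace the bracketed rule with wording such as: *the latest available post-procedure MR grade, including the discharge echocardiogram where one exists, is carried forward to 30 days.* Start the tipping-point analysis from the count this gives. Leave the endpoint definition unchanged, and do not add a rule that fails a lost patient for any earlier grade above moderate.

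Because enrolment is complete, also report which rule was applied to the primary analysis and whether any lost patient had a discharge grade above moderate. If none did, the two readings give the same count and the matter is closed.

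The cost is one sentence of analysis wording and a short disclosure. No new data are needed, since the discharge echo is already scheduled. The downside is that the reported success rate may be slightly lower.
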